6.3 General Concomitant Medication and Supportive Care Guidelines

All medications that are administered during the study must be recorded in the patient's CRF and in the source documents. Concomitant medications for other medical conditions are permitted as clinically indicated subject to approval by the study chair.

Subjects will be advised to use contraceptive precautions to avoid pregnancy during the treatment phase since the effects of investigational agents on sperms and embryos are unknown.

6.4 Duration of Therapy and Criteria for Removal from Study

Duration of treatment portion of the study (excluding screening time) will be approximately 85 Days (± 7 days). By signing the informed consent form and agreeing to participate in this study, the subjects are required to participate in entirety up to the completion of all scheduled visits and study procedures, or until one of the following criteria applies:

- A protocol violation occurs
- Disease progression occurs

- A serious or intolerable adverse event occurs (that in the opinion of the Investigator, requires the subject's discontinuation)
- The Investigator withdraws the subject (at the Investigator's discretion for reasons other than the adverse event)
- The Principle Investigator terminates the protocol
- The subject requests to be discontinued from the protocol
- The subject is lost to follow-up
- Intercurrent illness that prevents administration of ^{177}Lu -J591 or ^{177}Lu -PSMA-617
- Previous anaphylactic reaction to any J591 product or PSMA peptides/ligands

The investigators or physicians may stop the protocol or terminate a subject's participation in the protocol at any time should they judge:

- That it is not in the subject's best interest to continue
- If the subject experiences a protocol-related injury
- If the subject needs life-saving medications/procedures/treatment
- If the subject does not comply with the study plan
- General or specific changes in the patient's condition render the patient unacceptable for further treatment in the judgment of the investigator

They may also remove the subject from the study for various other administrative and medical reasons. They can do this without the patient's consent.

6.5 Duration of Follow Up

Patients will be followed until death for survival assessment. Patients removed from study for unacceptable adverse events will be followed until resolution or stabilization of the adverse event.

7. DOSING DELAYS/DOSE MODIFICATIONS

There will be no dosing modifications. Unless there are specific reasons not to do so, all patients who are eligible for the trial will receive 5 ± 2 mCi (185 ± 74 MBq) of ^{68}Ga -PSMA-HBED-CC during the screening visit and the Efficacy/Scan visit. During the treatment phase, the subject will receive ^{177}Lu -J591 + ^{177}Lu -PSMA-617 x 2 doses, 2-weeks apart based on the dose-level/Cohort to which he is assigned. The study chair must clear any dosing delays due to logistical issues (e.g. subject scheduling and/or radionuclide shipping that fall outside of the treatment window).

8. PHARMACEUTICAL INFORMATION

A list of the adverse events and potential risks associated with *Investigational Agent* can be found in **Section 13**.

8.1. Investigational Agent

A. ¹⁷⁷Lu–J591:

The humanized monoclonal antibody–huJ591 is provided by [name]. Radionuclide conjugation will be done at the Division of Nuclear Medicine, Department of Radiology, Weill Cornell Medicine.

The DOTA–J591 antibody molecule is labeled with radiometal ¹⁷⁷Lu in 1.0 M ammonium acetate buffer at pH 7.0. The radiolabeled J591 complex is then purified using size–exclusion column chromatography. To avoid the effects of autoradiolysis on the antibody, reaction time is minimized and the radiolabeled antibody preparations are formulated in phosphate buffered saline containing not more than 1% Human Serum Albumin (HSA). All reagents used in the conjugation and purification of J591 are made with pyrogen–free water. Radiolabeled J591 is periodically tested for sterility and pyrogenicity.

Each patient dose will be supplied to the study site on the day of or day before treatment by the central radiopharmacy. The J591 mAb is a deimmunized monoclonal antibody directed at the extracellular domain of human PSMA. For additional details, see Section 1. Radiolabeled antibody preparations are formulated in phosphate buffered saline containing not more than 1% Human Serum Albumin (HSA). In order to radiolabel J591 with β^- emitting radionuclides, the antibody molecule is first conjugated to a macrocyclic chelating agent, 1,4,7,10–tetraazacyclododecane–N,N',N'',N'''–tetraacetic acid (DOTA) by direct coupling of one of the four carboxylic acid groups of DOTA to the primary amines present in the protein structure. The radiolabeling of J591 with ¹⁷⁷Lu is achieved by adding the radionuclide to the ammonium acetate buffered J591. To avoid the effects of autoradiolysis on the antibody, reaction time is minimized and the reaction mixture is purified with a size exclusion column prior to administration. All reagents used in the conjugation and purification of J591 are made from pyrogen–free water. Radiolabeled J591 is tested periodically for sterility and pyrogenicity. Labeling efficiency and radiochemical purity will be determined using ITLC. Immunoreactivity of radiolabeled J591 mAb preparations will be determined using PSMA+ LNCaP tumor cells.

The material produced are subjected to quality assurance testing as outlined in the Food and Drug Administration “Points to Consider”. All production data and supporting documents, together with the results of all quality assurance testing, have been provided to and reviewed by the Food and Drug Administration (¹⁷⁷Lu–J591, IND# **11613**).

B. ^{177}Lu -PSMA-617 and ^{68}Ga -PSMA-HBED-CC:

PSMA-617 will be obtained from Endocyte (West Lafayette, LA) and PSMA-HBED-CC will be obtained from ABX Advanced Biochemical Compounds, Radeberg, Germany and will be shipped to and stored at WCM as per manufacturer's guidelines. Upon subject's enrollment and confirmation of date of infusions, these peptides will be labeled with Lutetium-177 or Gallium-68, respectively.

The material produced are subjected to quality assurance testing as outlined in the Food and Drug Administration "Points to Consider". All production data and supporting documents, together with the results of all quality assurance testing, have been provided to and reviewed by the Food and Drug Administration (^{177}Lu -PSMA-617, IND # 131966 and ^{68}Ga -PSMA-HBED-CC, IND# 124495).

8.2. Availability

^{177}Lu -J591 (IND# 11613), ^{177}Lu -PSMA-617 (IND# 131966) and ^{68}Ga -PSMA-HBED-CC (IND# 124495) are investigational agents supplied to investigators by Weill Cornell Medicine.

8.3. Agent Ordering

Upon enrollment of the subject, the WCM Study Coordinator will be notified about the ^{177}Lu -J591, ^{177}Lu -PSMA-617 and ^{68}Ga -PSMA-HBED-CC infusion dates. The WCM Study Coordinator will arrange with the staff of Nuclear Medicine Division at WCM for the timely labeling and delivery of the radiolabeled PSMA peptides to the site of infusion. The dates for study visits will be confirmed with the subject, site of infusion, and site of imaging.

8.4. Agent Accountability

The investigator, or a responsible party designated by the investigator, will maintain a careful record of the inventory and disposition of all agents received from Sponsor on a Drug Accountability Record Form (DARF).

9. CORRELATIVE/SPECIAL STUDIES

9.1 Laboratory Correlative Studies

9.1.1 CTC immune analysis:

Whole blood samples (2.7 mL in each vial) in two 4.5 mL 2.3% sodium citrate tubes (light blue top tube) will be collected for research analysis at specified time points (Screening/baseline and efficacy visit). These samples are collected for research purposes only and will not be billed to the subject. CTC will be stained for calreticulin analyzed for research purposes only.

9.1.2 Cell-Free Plasma DNA:

Peripheral blood will be collected in two 10 mL Cell-Free DNA BCT[®] tubes (Streck) at the specified time points (screening or pre-treatment and efficacy visit). These samples are collected for research purposes only and will not be billed to the subject. The cell-free plasma DNA will be analyzed for genomic studies and to identify DNA repair and AR-pathway alterations.

9.1.3 Immune Assay:

Serum samples will be obtained during screening prior to treatment and at the main efficacy visit for immune biomarkers and processed as per the lab manual. Results of these assays will not be billed to the patient and are for research purposes only.

9.1.4 Archival tissue:

Archival tissue will be requested during the screening visit. Fifteen unstained slides containing tumor material from archival paraffin-embedded tissue should be obtained. If available, metastatic tissue is preferred to prostate biopsy/prostatectomy specimens. The tissue will be analyzed for PSMA expression and DNA damage repair pathways for research purposes only.

9.2. Special Studies

Conventional Imaging studies as well as ⁶⁸Ga-PSMA-HBED-CC PET/CT imaging and Lutetium-177 Planar/SPECT imaging will be performed as described in schedule as well as clinically indicated to assess disease response. In subjects enrolled in this study, the measurable disease response will be calculated using Response Evaluation Criteria in Solid Tumors (RECIST Version 1.1) with PCWG3 modifications.

10. MEASUREMENT OF EFFECT

10.1 CTC count response

All subjects in this study will get blood samples drawn (at screening and EOS visit) for CTC enumeration by CellSearch methodology. Our primary analysis will assess those whose CTC counts drop to less than 5 or stay below 5 (responders) vs. those who remain at least 5 or above (non-responders) at EOS visit.

In addition, it appears that decreases in CTC counts with therapy are a favorable marker even if the count remains at least 5. We will also analyze % changes in CTC counts with at least 50% decline in CTC count from baseline considered a response at 12 weeks. Best response will also be analyzed (% increase or best % decrease at any point will also be reported in a waterfall plot).

As reported in phase III studies of men with mCRPC, a favorable CTC count and LDH level at 12 weeks has been associated with overall survival. We will report the proportion of subjects who have CTC count <5 and normal LDH at the efficacy (scan) visit time point.

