Men with progressive metastatic CRPC received 2 fractionated doses two weeks apart. Initially, 6 cohorts of 3–6 pts got 2 doses of ¹⁷⁷Lu–J591 2 wks apart (20 mCi/m², escalating to 45 mCi/m² x2). Subsequently, pts enrolled in 2 expansion cohorts at the recommended phase 2 doses (RP2D). Planar ¹⁷⁷Lu–J591 imaging was semi–quantitatively scored. The endpoints were PSA changes and survival (OS); as well as CTC count (CellSearch) changes in the expansion cohorts. 49 patients, with median age 74.1 years (range 55–95), median PSA of 44.9 ng/mL (1.9–766.5); 83.7% with bone, 61.2% with lymph node, 40.8% with visceral metastasis. 8.2% were CALGB (Halabi) low, 34.7% were intermediate, 57.1% were in high–risk group. RP2D’s of fractionated ¹⁷⁷Lu–J591 were 40 mCi/m² x2 or 45 mCi/m² x2 with option for GCSF. PSA changes for the low dose group were reported as 6.3% showing >50% PSA decline, 12.5% reporting >30% PSA decline, and 37.5% with any PSA decline. within RP2D group 21.2% showing >50% PSA decline, 42.4% reporting >30% PSA decline, and 66.7% with any PSA decline. The median overall survival for low dose group was 14.6 months and for RP2D group was 27.7 months. Accurate targeting of ¹⁷⁷Lu–J591 was seen in 79.6%. Patients with lower PSMA expression by imaging were less likely to respond (p=0.07). Of 25 with CTC counts, 14 declined, 8 stably favorable, and 3 increased. RP2D was associated with more PSA declines (p=0.036) and longer OS (p=0.004), even after controlling for CALGB prognostic grouping (adjusted HR 0.42 [95% CI 0.21, 0.84] p=0.01). Predictable, reversible myelosuppression was seen. 36 (73.5%) patients had grade 3/4 heme toxicities; 19 (57.6%) had Grade 4 heme toxicities in RP2D cohorts with 45.4% receiving prophylactic platelet transfusions (median 1, range 1–4) and 6 GCSF. 14 (28.6%) had infusion reactions (without pre–meds), with 1 patient having Grade 2 infusion reaction leading to withdrawing from the study prior to his 2nd dose. 5 (10.2%) had transient Gr 1/2 AST/ALT. This study concluded that fractionated ¹⁷⁷Lu–J591 is well tolerated with predictable, reversible myelosuppression and PSA and CTC declines. Additionally, with dose–fractionation, the cumulative dose MTD is 14–28% higher than single dose MTD with similar toxicity.

Table 1: Toxicities data from Phase 2 single dose ¹⁷⁷Lu–J591 Study and Phase 1 fractionated ¹⁷⁷Lu–J591 study:

| | Single Dose | Fractionated Dose |
|--|-------------|-------------------|
|--|-------------|-------------------|

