Circulating tumor cell (CTC) counts via the FDA-cleared, standard of care CellSearch platform were demonstrated to be prognostic in men with advanced prostate cancer prior to systemic therapy and a "conversion" from an unfavorable count (≥ 5 CTCs/7.5 mL) was associated with a median similar to those starting with favorable counts, leading to clearance of this particular test by the FDA (109). More recently, the combination of CellSearch CTC enumeration and serum LDH have been demonstrated to have prognostic value, meeting Prentice criteria for survival surrogacy in the setting of abiraterone/prednisone treatment in men with mCRPC previously treated with docetaxel (110)

iii. Immune Assays:

We and others have observed some durable responses following radiolabeled-PSMA therapy. Radiation may lead to an induction of or increase in immune responses to locally expressed antigens, but unlike external beam radiation, PSMA-targeting generally delivers radiation to all sites of disease (by imaging) and therefore observing an abscopal response is not possible. In prostate cancer, humoral immune response has already been documented with immunotherapy. *We hypothesize that prostate cancer is immunogenic following PSMA-targeted radiation, and that the serological repertoire in patients may be useful as a pharmacodynamic, prognostic, or even predictive tool.*

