- c: Any subject with grade ≥2 neutropenia or thrombocytopenia at Treatment 2 will initially not be eligible to receive the second ¹⁷⁷Lu-J591 / ¹⁷⁷Lu-PSMA-617 infusions. The dose will be held until the toxicity has resolved to grade 1 for a maximum of 2 weeks. If the toxicity has not resolved after 2 weeks, the dose will be discontinued.
- d: CMP (with direct bilirubin in subjects with known Gilbert’s syndrome)
- e: CTC enumeration via CellSearch methodology may be obtained during screening or prior to treatment C1D1
- f: CTC collection for research purposes may be performed during screening or prior to treatment C1D1: two 2.3% sodium citrate “light blue top” tubes
- g: Cell-Free DNA BCT[®] may be obtained during screening or prior to treatment C1D1 and will be whole blood collection in a tube intended for collection, stabilization and transportation of cell-free plasma DNA. 10 mL tube will be used for collecting whole blood for research purposes
- h: Radiographic evaluation will include bone scan, CT/MRI of abdomen/pelvis, and Chest x-ray (CXR waived if CT/MRI includes chest). Following mandatory repeat imaging with Scan/Efficacy visit, continued repeat imaging is recommended approximately 12 weeks until radiographic progression as part of standard care.
- i: Planar/SPECT imaging one week after the ¹⁷⁷Lu-PSMA-617 1st dose infusion in all subjects. Optional imaging will be performed on consenting subjects between D1-D4 and/or prior to treatment #2 on D15.
- j: Survival assessment and relevant medical history to be collected until death
- k: Short-term follow up to be completed q4 weeks following the scan visit until 6 months from the 1st treatment visit. Subjects who are progression-free at 6 months will continue with q4-week labs and q12-week standard imaging per guidelines (as in h above).
- l: PRO = patient reported outcomes = BPI-SF and FACT-P; to be performed at time points specified during treatment phase, then q12 weeks (at imaging time points) during short-term follow up until radiographic progression
- m: serum for immune assays; 1 sample to be collected at any time during screening prior to treatment #1, then again during scan/efficacy visit

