- PSA (Follow up visits 2 & 4)
- LDH (Follow up visits 2 & 4)
- Adverse event evaluation
- Concomitant medications

6.1.2.3 Follow-up lab visits: Follow up Visit 3 (Day 43 \pm 3); Follow up Visit 5 (Day 71 \pm 3)

- CBC with differential and platelet count
- CMP (with direct bilirubin with known Gilbert's syndrome)
- PSA
- LDH

Lab visits may be performed at any CLIA certified lab

6.1.3. Efficacy Evaluation (scan) Visit (Day 85 ± 7; note that these study procedures are not expected to occur on a single day)

The following procedures must be completed during the efficacy visit(s):

- Targeted Physical Examination with vital signs and weight
- Medical History
- Brief Pain Inventory, FACT-P
- ECOG Performance Status
- CBC with differential and platelet count
- CMP (with direct bilirubin with known Gilbert's syndrome)
- PSA
- LDH
- Testosterone
- CTC count via CellSearch methodology
- CTC for research
- Cell-Free DNA BCT[®] Research blood sample
- Immune research blood sample
- Same standard radiographic imaging modality as baseline (CT/MRI and bone scan +/- CXR)
- Single intravenous dose of ⁶⁸Ga-PSMA-HBED-CC (5±2mCi or 185±74MBq)
- PET/CT scan will be obtained between 1 and 3 hours post-injection of ⁶⁸Ga-PSMA-HBED-CC
- Adverse event evaluation
- Concomitant medications
- Concomitant procedures

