10.4 Duration of CTC response

Duration of CTC response is defined from the first CTC count drop to <5 (or $\leq 50\%$ of baseline) to the time CTC count increases to ≥ 5 (or $\geq 25\%$ increase from nadir).

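### The main CTC response rate counts patients who start and stay below 5, so it measures week-12 favorable status and shifts with baseline case mix; CTC duration and best change lack the scheduled samples they need

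*Combined protocol and SAP*

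**What the plan says.** Section 10.1 compares patients "whose CTC counts drop to less than 5 or stay below 5 (responders" with "those who remain at least 5 or above (non-responders) at EOS visit". It calls this the primary CTC analysis. The same section adds percent change in CTC count, a decline of at least 50% from baseline as a further response, a waterfall plot of best change at any point, and the proportion with CTC below 5 and normal LDH at the efficacy visit. The efficacy analysis text in Section 10.8 reports the CTC response proportion as a binomial proportion with a 95% confidence interval. Section 12.5.2 makes it a descriptive secondary analysis.

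On timing, Section 10.1 has blood drawn "at screening and EOS visit) for CTC enumeration by CellSearch methodology". Footnote e of Table 15 gives two options for the single baseline sample: "CTC enumeration via CellSearch methodology may be obtained during screening or prior to treatment C1D1". The only post-treatment entry is at the efficacy visit (Section 6.1.3, Day 85 ± 7), which Section 12.5.1 equates with the end-of-study visit. The procedures for short-term and long-term follow-up (6.1.4 and 6.1.5) list no CTC count.

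Section 10.4 nevertheless states: "Duration of CTC response is defined from the first CTC count drop to <5", or to half of baseline or less, and it runs until a later rise.

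**The concern.** A measure labelled response should reflect change after treatment. Under 10.1, a patient who enters below 5 and stays there raises the rate just as a converter does. No criterion in Sections 3.2 or 3.3 requires a baseline count of 5 or more, and no analysis restricted to such patients is specified. The secondary objective in Section 1.2 lists changes in CTC count separately from the rate of favorable CTC and LDH; the main analysis measures the second kind of quantity and labels it as the first. Two cohorts with the same conversion rate could then show different CTC response rates only because their baseline counts differed.

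Two smaller gaps follow. A patient who worsens from below 5 to 5 or more has not dropped, has not stayed below and has not remained above, so an analyst could leave him out of the denominator. And two further CTC measures need data that the schedule does not supply.

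**Working it through.** **Inputs**

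- The plan states no expected CTC response rate and no expected share with baseline CTC below 5, so there is no planned figure to reproduce.
- The only relevant figure is from the fractionated J591 study in Section 2.3.1.2 (iii): "Of 25 with CTC counts, 14 declined, 8 stably favorable, and 3 increased". The counts add up: 14 + 8 + 3 = 25.
- Phase II enrolls at most 27 patients (Section 12.2).

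**Stably favorable share.** 8/25 = 32.0%, with exact (Clopper-Pearson) 95% CI 14.9 to 53.5%.

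**What the 10.1 proportion estimates.** Let b be the share with baseline CTC below 5, s the share of those still below 5 at week 12, and c the conversion rate among patients with baseline 5 or more. Then

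R = b·s + (1 − b)·c.

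The documents give none of b, s or c for this trial. I take 32% and its interval as an assumed b, and 50 to 100% as an assumed s. Strictly, 8/25 counts patients who started and stayed favorable, so it is closer to b·s than to b. Using it as b with s below 1 extends the range downward.

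*No conversions (c = 0), so R = b·s:*

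| b | s = 1 | s = 0.9 | s = 0.75 | s = 0.5 |
|---|---|---|---|---|
| 14.9% | 14.9% | 13.4% | 11.2% | 7.4% |
| 32% | 32% | 28.8% | 24% | 16% |
| 53.5% | 53.5% | 48.2% | 40.1% | 26.8% |

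With nobody converting, the reported response runs from about 7% to about 54%.

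*Same conversion rate, different case mix (c = 0.2, s = 0.9, both assumed):*

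- b = 14.9%: R = 0.149 × 0.9 + 0.851 × 0.2 = 30.4%
- b = 32%: R = 0.32 × 0.9 + 0.68 × 0.2 = 42.4%
- b = 53.5%: R = 0.535 × 0.9 + 0.465 × 0.2 = 57.4%

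**Illustration with 27 patients, 9 of whom start and stay below 5 (exact 95% CI):**

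| Conversions among the other 18 | Conversion rate | Proportion under 10.1 |
|---|---|---|
| 0 | 0/18 = 0% (0 to 18.5%) | 9/27 = 33% (16.5 to 54.0%) |
| 6 | 6/18 = 33% (13.3 to 59.0%) | 15/27 = 56% (35.3 to 74.5%) |

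**Sampling.** Duration under 10.4 needs one count to show the drop and a later one to show the rise, so at least two after baseline. The schedule has one. The number of patients with an observable start and end from scheduled samples is therefore zero. On the below-5 criterion, a patient who was below 5 throughout also has no drop from which to start the clock. With one post-baseline value, the best change at any point is the week-12 change.

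**The case against.** The strongest case for the plan is that grouping by week-12 status is deliberate. Section 2.9 refers to conversion "from an unfavorable count", but says that converters had a median similar to that of patients who started favorable, which is a reason to group the two. Section 1.2 names favorable CTC and LDH at 12 weeks as a target. This stands, and it is why the below-5 proportion should be kept. It does not justify calling that proportion a response rate, or leaving conversion unreported.

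The analysis of a 50% or greater decline gives no credit for an unchanged favorable count and so mitigates part of the problem. It is not the designated main CTC analysis, and percent change is undefined for a baseline count of zero.

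It is also fair that no hypothesis, power calculation or go/no-go rule uses CTC (phase II rests on PSA decline), and that CTC duration appears in neither the objectives nor the listed analyses. A patient at 5 or more at the final visit would most naturally be read as a non-responder, so that gap is one of wording.

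A reader might infer that about a third of patients would be responders with no treatment effect. The documents do not support this. The 25 patients were all treated, the interval is wide, and nothing shows how many untreated counts would stay below 5; holding a low count may itself reflect treatment. A reader might also compute (14 + 8)/25 = 88% as a ceiling, and 8/22 = 36% as the share of those responders who were never unfavorable. Both need baseline and final counts that Section 2.3.1.2 does not give: some of the 14 may have started below 5, and some of the 3 whose counts rose may have stayed below 5. Finally, duration is better described as unscheduled than as impossible. Section 2.9 calls CellSearch standard of care, so off-schedule counts may exist, but they would not be systematic.

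**Conclusion.** The concern holds as a minor point of definition. The main CTC proportion is week-12 favorable status, depends on the baseline share below 5, and should not be presented as response to treatment. That conclusion comes from the wording of 10.1 and needs no numerical assumption. Its size does: roughly 7 to 54% apparent response with zero conversions rests on applying an interval from another treated single-agent cohort to this trial's baseline mix and on assuming that 50 to 100% stay below 5. Duration of CTC response cannot be estimated as defined from the scheduled samples, and best change at any point adds nothing to the week-12 change. The secondary, descriptive role of the endpoint and the planned 50%-decline analysis keep the consequence small.

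**What to change.** - In 10.1, keep CTC below 5 at week 12, but name it favorable status.
- Report conversion (5 or more at baseline, below 5 at week 12) with patients at 5 or more at baseline as the denominator.
- Report separately the proportion who remained favorable among those below 5 at baseline.
- State that a rise from below 5 to 5 or more is non-response and stays in the denominator.
- Delete 10.4 and the at-any-point wording, or limit both to the single 12-week change.

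These are text changes that use counts already planned. The cost is precision for conversion: if 32% start favorable, the denominator falls from 27 to 27 × 0.68 = 18.4, about 18. Over the interval for b it runs from 27 × 0.465 = 12.6 to 27 × 0.851 = 23.0, so about 13 to 23. The confidence interval for conversion widens accordingly.

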Men with progressive metastatic CRPC received 2 fractionated doses two weeks apart. Initially, 6 cohorts of 3–6 pts got 2 doses of ^{177}Lu -J591 2 weeks apart (20 mCi/m², escalating to 45 mCi/m² x2). Subsequently, pts enrolled in 2 expansion cohorts at the recommended phase 2 doses (RP2D). Planar ^{177}Lu -J591 imaging was semi-quantitatively scored. The endpoints were PSA changes and survival (OS); as well as CTC count (CellSearch) changes in the expansion cohorts. 49 patients, with median age 74.1 years (range 55–95), median PSA of 44.9 ng/mL (1.9–766.5); 83.7% with bone, 61.2% with lymph node, 40.8% with visceral metastasis. 8.2% were CALGB (Halabi) low, 34.7% were intermediate, 57.1% were in high-risk group. RP2D's of fractionated ^{177}Lu -J591 were 40 mCi/m² x2 or 45 mCi/m² x2 with option for GCSF. PSA changes for the low dose group were reported as 6.3% showing >50% PSA decline, 12.5% reporting >30% PSA decline, and 37.5% with any PSA decline. within RP2D group 21.2% showing >50% PSA decline, 42.4% reporting >30% PSA decline, and 66.7% with any PSA decline. The median overall survival for low dose group was 14.6 months and for RP2D group was 27.7 months. Accurate targeting of ^{177}Lu -J591 was seen in 79.6%. Patients with lower PSMA expression by imaging were less likely to respond (p=0.07). Of 25 with CTC counts, 14 declined, 8 stably favorable, and 3 increased. RP2D was associated with more PSA declines (p=0.036) and longer OS (p=0.004), even after controlling for CALGB prognostic grouping (adjusted HR 0.42 [95% CI 0.21, 0.84] p=0.01). Predictable, reversible myelosuppression was seen. 36 (73.5%) patients had grade 3/4 heme toxicities; 19 (57.6%) had Grade 4 heme toxicities in RP2D cohorts with 45.4% receiving prophylactic platelet transfusions (median 1, range 1–4) and 6 GCSF. 14 (28.6%) had infusion reactions (without pre-meds), with 1 patient having Grade 2 infusion reaction leading to withdrawing from the study prior to his 2nd dose. 5 (10.2%) had transient Gr 1/2 AST/ALT. This study concluded that fractionated ^{177}Lu -J591 is well tolerated with predictable, reversible myelosuppression and PSA and CTC declines. Additionally, with dose-fractionation, the cumulative dose MTD is 14–28% higher than single dose MTD with similar toxicity.

Table 11: Toxicities data from Phase 2 single dose ¹⁷⁷Lu–J591 Study and Phase 1 fractionated ¹⁷⁷Lu–J591 study:

| | Single Dose | | Fractionated Dose | | |

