Median bPFS, rPFS, and OS, including survival curves, will be estimated using Kaplan-Meier methodology. Greenwood's formula will be used to calculate 95% confidence intervals for the Kaplan-Meier estimates. Percent change in PSA from baseline will be described by mean/median and standard deviation/inter-quartile range, as appropriate, depending on the distribution of percent change from baseline. Modified RECIST response (i.e., CR, PR, and CR/PR proportions), CTC count response proportion, defined favorable LDH/CTC proportion, and associated 95% confidence intervals, will be estimated via binomial proportions.

All subjects will be offered optional but recommended baseline and subsequent ⁶⁸Ga-PSMA-HBED-CC PET/CT, and those treated with ¹⁷⁷Lu-labeled products will undergo Planar/SPECT imaging. We will analyze the data for associations with response to treatment as well as survival by chi-square tests/Fisher's exact tests and log-rank tests, respectively. For pre/post imaging comparisons, McNemar's chi-square test and paired t-tests/Wilcoxon signed-rank tests will be used, as appropriate. We plan to report data for each individual study as well as across the studies.

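### The ≥50% CTC-decline response rule (10.1, and its counterpart in 10.4) has no minimum baseline count, so one-cell changes in men starting at 1–4 cells can score as responses

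*Combined protocol and SAP*

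**What the plan says.** Section 10.1 has all subjects give "blood samples drawn (at screening and EOS visit) for CTC enumeration by CellSearch methodology", and Table 15 likewise schedules one baseline count and one count at the efficacy visit. The main CTC analysis classes a man as a responder if his count falls below 5 or stays below 5 at the end-of-study visit. The section then argues that "decreases in CTC counts with therapy are a favorable marker even if the count remains at least 5" and on that basis adds a percentage rule, "with at least 50% decline in CTC count from baseline considered a response at 12 weeks", plus a waterfall plot of percent changes.

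Section 10.4 uses the same percentage criterion for duration: "Duration of CTC response is defined from the first CTC count drop to <5", or alternatively to half of baseline or less. The efficacy analysis at the end of 10.8 says that the "CTC count response proportion, defined favorable LDH/CTC proportion, and associated 95% confidence intervals, will be estimated via binomial proportions".

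None of 10.1, 10.4, 10.8 or 12.5.2 gives a minimum baseline, a minimum absolute change or a convention for a baseline of 0. The eligibility criteria set no CTC threshold. Section 2.9 gives the protocol's own cut: 5 or more CTCs per 7.5 mL is unfavorable.

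**The concern.** The rule is wider than its reason. It was introduced for men whose count stays at 5 or more, but as written it also scores men who start at 1, 2, 3 or 4 cells. At those counts a 50% fall can be a change of one cell in a single tube, which is well within counting variation.

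Such men are likely to be enrolled. Section 2.7 reports from the group's earlier fractionated-dose trial: "Of 25 with CTC counts, 14 declined, 8 stably favorable, and 3 increased".

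The protocol guards against this problem for PSA. Sections 10.3, 10.5 and 10.7 pair the percentage with an absolute change of 2 ng/mL, and 10.2 requires a confirming value. The CTC percentage rule has neither safeguard.

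At stake is how to read one supplementary response proportion and one plot within a secondary objective. Part of what they show would be noise in low-count men, and men at 0 would be handled by a choice made after the data are seen.

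**Working it through.** The plan states no error rate or expected proportion for this rule, so there is no figure of its own to reproduce.

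**1. Literal scoring.** Percent decline = (baseline − week 12) / baseline.
- 1 to 0: 1/1 = 100%, response.
- 2 to 1: 1/2 = 50%, response.
- 4 to 3: 1/4 = 25%, no response.
- 1 to 3: a 200% increase in the waterfall plot.
- 0 to anything: division by zero, so no percent change.

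**2. Chance response at a given baseline.** Assumption (not from the documents): the week-12 count F is Poisson, nothing has truly changed, and the true mean equals the observed baseline b. A response is F ≤ b/2.
- b = 1: P(F = 0) = e⁻¹ = 36.8%
- b = 2: P(F ≤ 1) = e⁻²(1 + 2) = 40.6%
- b = 3: P(F ≤ 1) = e⁻³(1 + 3) = 19.9%
- b = 4: P(F ≤ 2) = e⁻⁴(1 + 4 + 8) = 23.8%
- b = 5: 12.5%; b = 6: 15.1%; b = 10: 6.7%; b = 20: 1.1%

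The range at 1–4 cells is therefore 20–41%.

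**3. Same question with both counts random.** Let baseline B and week-12 count F be independent Poisson with the same mean L, and condition on B being 1 to 4:

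P = Σ_{b=1..4} P(B = b) · P(F ≤ b/2) / Σ_{b=1..4} P(B = b).

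For L = 1 the denominator is 0.628 and the numerator 0.330, giving 52.5%. For L = 2, 3 and 4 the results are 34.6%, 21.9% and 13.0%.

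**4. Sensitivity at 1–4 cells.** Treating the true mean as uncertain given the observed count (negative-binomial predictive) gives 19–31% with a flat prior and 31–50% with a 1/L prior. Extra-Poisson variation raises the rates: with variance μ + μ² and the mean at the observed count they are 44–56%. In the step 3 model, means outside 1–4 widen the range to 68% (L = 0.5) and 7% (L = 5).

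**5. Effect on the overall proportion.** Assumption: the 8 of 25 stably favorable men (32%) stand for the share starting below 5. The contribution is 0.32 × P(response | B < 5), with a baseline of 0 counted as non-response.
- L = 1: 0.32 × 0.331 = 10.6 points
- L = 2: 0.32 × 0.296 = 9.5 points
- L = 3: 0.32 × 0.206 = 6.6 points
- L = 4: 0.32 × 0.126 = 4.0 points
- L = 0.5: 8.5 points; L = 0.1: 2.8 points; L = 0.05: 1.5 points

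As L approaches 0 the contribution vanishes. The documents do not say how many of the 8 men were at 0 and how many at 1–4, so the range is from near 0 to about 11 points.

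**The case against.** The strongest reply is that little depends on this rule. It is introduced as an addition to the main CTC analysis, 12.5.2 treats CTC response descriptively, and the phase II decision rests on PSA. A man at 1–4 cells who meets the percentage rule ends at 2 or fewer, so the main rule already counts him as a responder. The sentence before the rule also points to the intended population. All of this stands and limits the weight of the point. It does not remove it: the rule as written covers everyone, and 10.4 repeats the criterion without a floor.

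Three stronger readings are tempting but unsupported.
- A reader might infer that noise adds at least 4 points to the overall response proportion. That holds only if every low-count man has a true mean of 1 to 4, and the documents give no such split.
- A reader might infer that men with a baseline of 0 must leave the denominator. Under the binary rule they can be read as non-responders, since a count of 0 cannot fall. Only the waterfall value is truly undefined.
- A reader might infer that the floor has to be 10, because a fall of at least 50% leaves 5 or more cells only from a baseline of 10 (10 to 5, but 9 to 4 or fewer). The arithmetic is right, but the documents' cut is 5. A floor of 10 would drop men at 5–9 from the waterfall, so a fall from 9 to 5, which is not a conversion, would be shown nowhere.

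**Conclusion.** The point holds as a modest defect in a supplementary, descriptive analysis. The percentage rule in 10.1 and 10.4 lacks a baseline floor and so departs from its own rationale. Chance alone could make 20–41% of men at 1–4 cells responders, or 13–52% under the alternative conditioning. These figures rest on an assumed Poisson model with no true change, but the conclusion does not depend on one version of it.

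The size of the effect on the overall proportion is not determined by the documents. Nothing here supports a claim that the main <5 rule, the favorable CTC/LDH proportion or the phase II conclusion is compromised.

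**What to change.** In 10.1, limit the ≥50% decline response, its denominator and the percent-change waterfall to subjects with a baseline CTC count of at least 5 per 7.5 mL. Report subjects with baseline below 5, including 0, by absolute counts and by whether they stay below 5. Put the same floor on the half-of-baseline clause in 10.4 so that the two sections agree.

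This takes a sentence or two in each section, with no new samples, visits or patients. The downside is fewer men in the percent-change analysis: if 32% start below 5, about 9 of 27 (0.32 × 27 = 8.6).

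The floor reduces the noise but does not remove it. At a baseline of 5 the chance rate is still 12.5%, or 14–23% if the true mean is treated as uncertain, so showing the absolute counts beside the percentages is worthwhile.
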